# 8.5 Safety Monitoring

Toxicities will be monitored using CTCAE 4.03 criteria, with a focus on recording immune-related adverse events (irAE) (9). Stopping rules will be based on an expected irAE rate of 15-20%, where 10-15% had grade 3-4 irAE in one study (38) and in another 19% had grade 3, and 3.2% grade 4 irAEs (59). Significant increases over these rates are not expected but would be a reason for early discontinuation. Thus, formal safety bounds based upon the observed number of participants who experience a DLT as defined in Section 9.9 will guide decisions about early stopping due to potential safety concerns (Table 8). The definition of

DLT considers both irAEs and previously reported DLTs related to vaccine. If a stopping bound is crossed then accrual to the study will be suspended until the study PI, co-investigators and the DSMC can review the data, and determine if the study should continue, be amended or be closed to further accrual. The rate of DLTs will be monitored up to 30 days after the last vaccination. A sequential probability ratio test (SPRT) based upon a binomial test of proportions for DLTs will be used. Only the upper boundary will be used for monitoring to protect against excessive failure rates. The stopping boundary are for a SPRT contrasting a 15% versus 30% DLT rate, with nominal type I and II errors of 10% and 10%, respectively. The slope of the parallel lines for monitoring is 0.219 and the intercept for the upper bound is 2.476.

•	ie o. Otopping Oulde	
	Number of participants	Boundary
	4-6	≥4
	7-11	≥ 5
	12-15	≥6
	16-20	≥7
	21-25	≥ 8
	26-27	≥ 9

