# 9.9 **Dose-limiting Toxicities (DLT)**

#### 6MHP

A DLT of the 6MHP vaccine is defined as any unexpected Grade 3 or greater hematologic or non-hematologic toxicity that is definitely, probably, or possibly related to the administration of the vaccine. Small ulcerations of the skin at vaccine sites are expected. Thus, ulcerations will be considered DLTs only if the ulcers are  $\geq 2$  cm in diameter, require antibiotics or surgical debridement.

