# **Ipilimumab**

A DLT of ipilimumab is defined as any toxicity that is definitely, probably, or possibly related to the administration of ipilimumab and requires permanent discontinuation of ipilimumab.

If a DLT occurs and cannot be attributed to either the 6MHP or ipilimumab, then a DLT will be attributed to both.

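### The 15% null of the safety bound comes from grade 3-4 irAE rates, but Table 8 counts Section 9.9 DLTs, and no background rate is given for that event

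*Combined protocol and SAP*

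**What the plan says.** Section 8.5 gives the basis of the rule as "Stopping rules will be based on an expected irAE rate of 15-20%, where 10-15% had grade 3-4 irAE in one study (38", and adds that "in another 19% had grade 3, and 3.2% grade 4 irAEs (59". It does not expect significant increases over these rates, but says they would be grounds for stopping early.

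The same paragraph then moves to "formal safety bounds based upon the observed number of participants who experience a DLT as defined in Section 9.9". The design values are stated for that event: "The stopping boundary are for a SPRT contrasting a 15% versus 30% DLT rate", with nominal errors of 10% and 10%, slope 0.219 and upper intercept 2.476. DLTs are monitored to 30 days after the last vaccination. The only link offered between the two events is that the definition of "DLT considers both irAEs and previously reported DLTs related to vaccine".

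Section 9.9 has two limbs:

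- **Vaccine:** "any unexpected Grade 3 or greater hematologic or non-hematologic toxicity that is definitely, probably, or possibly related to the administration of the vaccine", plus ulcerations meeting stated criteria.
- **Ipilimumab:** "any toxicity that is definitely, probably, or possibly related to the administration of ipilimumab and requires permanent discontinuation of ipilimumab".

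A DLT that cannot be attributed to either agent is attributed to both. Section 9.1.2 defines an unexpected event as one not listed in Tables 3-6. Section 8.2.1 says the stopping rules are meant for toxicity beyond that expected with ipilimumab alone, and cites hypophysitis seen with two other vaccine combinations. The bound is applied overall and within cohort. Section 8.6 calls it non-binding.

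**The concern.** The benchmark and the counted event are different. The cited rates classify events by immune mechanism and severity. The ipilimumab limb of the DLT classifies them by a treatment consequence, with no grade threshold and no immune criterion. Neither set contains the other: a listed grade 3-4 irAE that does not end ipilimumab is not counted, while a lower-grade or non-immune toxicity that does end it is counted.

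Two things are at stake. First, the grade 3-4 irAE rate could rise above the cited figures, which 8.5 names as a reason to stop, without moving the count in Table 8. Second, 8.2.1 wants the rule to show excess over ipilimumab alone. Without a background rate for the counted event, neither crossing the bound nor staying below it can be read that way. Safety is a primary objective, and Table 8 is the only formal safety bound in the plan.

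**Working it through.** **1. Reproduce the plan's boundary.** Inputs from 8.5: p0 = 0.15, p1 = 0.30, alpha = beta = 0.10.

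- D = ln[p1(1-p0) / (p0(1-p1))] = ln[(0.30 × 0.85)/(0.15 × 0.70)] = 0.8873
- slope = ln[(1-p0)/(1-p1)] / D = ln(0.85/0.70)/0.8873 = 0.1942/0.8873 = 0.2188 (plan: 0.219)
- upper intercept = ln[(1-beta)/alpha] / D = ln(9)/0.8873 = 2.476 (plan: 2.476)
- bound at n = smallest integer not below 2.476 + 0.219n

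This matches Table 8 at 23 of the 24 values n = 4 to 27. The exception is n = 16, where 2.476 + 0.219 × 16 = 5.98 gives 6 and the table gives 7. The table is therefore essentially right for 15% versus 30%. The open question is whether 15% describes the event being counted.

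**2. Set the two events side by side.**

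| | Benchmark (8.5) | Counted event (9.9) |
|---|---|---|
| Mechanism | immune-related | vaccine limb: any type; ipilimumab limb: any related toxicity |
| Severity | cited at grade 3-4 | vaccine limb: grade 3 or more and unexpected, plus ulcerations; ipilimumab limb: no grade |
| Consequence | none required | ipilimumab limb: permanent discontinuation |
| Rate given | 15-20%; 10-15%; 19% + 3.2% = 22.2% (if no patient is counted twice) | none |

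As a check on the benchmark, the grade 3 and 4 entries in the irAE block of Table 5 sum to 66 + 4 = 70 events in 511 patients, or 13.7% at most, since one patient may have several. That agrees with the cited 10-15% and confirms that the benchmark is a severity rate. No section gives a DLT or discontinuation rate for ipilimumab 3 mg/kg, or converts the irAE rate into one.

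**3. Trace a typical irAE through the definitions.** Table 5 lists colitis, diarrhea, hepatitis, hypophysitis, hypopituitarism, adrenal insufficiency, rash and raised transaminases. Under 9.1.2 these are expected, so they cannot be vaccine DLTs at any grade. They count only through the ipilimumab limb, that is, only if ipilimumab is permanently discontinued. This includes hypophysitis, the signal named in 8.2.1. Section 1.6 also has a grade-specific convention (expected if seen in 4% of patients at that grade or higher), which would classify some of these differently. The plan does not say which convention governs the DLT count.

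**4. What the bound does at different true DLT rates.** Exact binomial recursion: after each participant, the probability mass at or above the Table 8 bound is removed, from n = 4 to n = 27.

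| True DLT rate | P(cross by n = 27) |
|---|---|
| 10% | 0.7% |
| 15% | 4.5% |
| 20% | 15% |
| 22.2% | 23% |
| 25% | 34% |
| 30% | 55% |

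Two readings, each resting on an assumed background rate:

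- If the background DLT rate were 10%, a doubling to 20% would trigger review 15% of the time.
- If it were 20-22.2%, accrual would be suspended 15-23% of the time with no excess toxicity.

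**5. How far the bound moves with p0** (same formulas, 10%/10% errors; contrasts chosen for illustration):

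| Contrast | Slope | Intercept | Bound at n = 27 |
|---|---|---|---|
| 10% vs 25% | 0.166 | 2.000 | 7 |
| 15% vs 30% (plan) | 0.219 | 2.476 | 9 |
| 20% vs 35% | 0.271 | 2.864 | 11 |

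At a true rate of 25%, the 10%-versus-25% bound is crossed 66% of the time and Table 8 34%. At a true rate of 30%, the 20%-versus-35% bound is crossed 29% of the time and Table 8 55%.

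**The case against.** The best defence is that the two events may largely coincide. Whether a grade 3-4 irAE ends ipilimumab depends on the practice guidelines, package insert and management guide to which 6.4.2 refers, and none of these is in the documents. The vaccine limb also admits unexpected grade 3 or greater events without discontinuation. So a reader who infers that Table 8 counts only ipilimumab discontinuations, or that no treated grade 3-4 irAE can count, goes further than 9.9 allows. This part stands. It limits how large the gap can be claimed to be, but it does not supply the missing rate.

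A reader might also infer that Table 8 is miscalculated or demonstrably miscalibrated. It is not miscalculated for 15% versus 30%, apart from n = 16. Miscalibration cannot be shown without a true DLT rate, and the error could run either way.

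Nor is 15% wrong because it is the bottom of 15-20% and below 22.2%. For a safety bound the lower null is the more cautious choice, and a null may be an acceptability threshold instead of a historical mean. Section 8.5, however, presents it as derived from the irAE rates.

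Finally, crossing only suspends accrual for review, the bounds are non-binding, and under 9.12 the DSMC meets monthly and reviews all adverse events. Irregular patterns of irAEs outside Table 8 can still be seen. That lowers the severity, but it leaves the formal rule without a stated reference for what it counts.

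**Conclusion.** The point holds in a limited form. Section 8.5 takes its null from grade 3-4 irAE rates and names a rise in those rates as a reason to stop, yet the bound counts a different event. Grade 3-4 irAEs of types listed in Tables 3-6 that do not end ipilimumab are left out under 9.1.2. The 15% null is therefore not supported for the event monitored.

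The documents do not establish whether the bound is too lax or too strict, or by how much. What they do show is sensitivity: over true DLT rates from 10% to 22.2% the crossing probability runs from 0.7% to 23%. These probabilities assume independent participants, a common DLT rate, a look after each participant and full accrual to 27. The background rates in the examples are assumptions.

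This should be fixed. It is not critical, because the bound is a non-binding review trigger with monthly committee oversight.

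**What to change.** Align the event and the null in 8.5 by one of two routes:

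- **Change what the bound counts.** For the stopping bound only, count participants with a grade 3-4 irAE or a 9.9 DLT, and state p0 from the plan's own 15-20% range with a sentence on why that value suits the combined event. Section 9.9 and its consequences for treatment stay as they are.
- **Keep the 9.9 DLT.** State a sourced background rate for it over the same window, to 30 days after the last vaccination. Whether the studies already cited report such a rate cannot be seen from the documents.

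Then recompute the slope, intercept and Table 8, and report exact crossing probabilities to n = 27 at p0, at p1 and at rates between. Say in the same paragraph whether 9.1.2 or the 4% convention decides what is unexpected, and reconcile the n = 16 entry while the table is open.

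The cost is one paragraph and one table. The downside is that the bound may become tighter or looser: about 7 to 11 at n = 27, depending on p0, against 9 now. The 10%-versus-25% figures above are an illustration under an assumed rate, not a recommended bound.

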#### 8.2 Evaluation of Sample Populations and Criteria

8.2.1 Safety

All participants receiving any protocol treatment will be evaluated for safety.

The 6MHP vaccine has been safe, with lower toxicities than with class I peptides, in particular with lower autoimmune or hyperimmune toxicities. Ipilimumab causes toxicities related to unmasking autoimmunity, some of which can be severe, but are managed well with steroids. We do not

anticipate increased autoimmune toxicities by combining 6MHP vaccine with ipilimumab, but relatively high rates of hypophysitis have been reported by combining ipilimumab with each of two other vaccines. Thus, this trial will be designed with stopping rules for toxicities beyond those expected with ipilimumab alone. Formal safety bounds (Section 8.5) based upon monitoring dose limiting toxicities (DLT) will guide decisions about early stopping due to potential safety concerns. If a stopping bound is crossed then accrual to the study will be suspended until the study PI, co-investigators and the DSMC can review the data, and determine if the study should continue, be amended or be closed to further accrual. The proposed safety bound will be applied overall and within cohort.

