# 8.3 Sample Size and Accrual

Target sample size is based upon having sufficient information to assess immunogenicity overall cohort conditional on safety bounds not being crossed. Observed immune response from arm D from our most current 6MHP protocol Mel63, provides the basis for sample size determination. Define immune response as 'at least two consecutive 10 fold' responses for 6MHP pool assessed in the blood. Results for Mel63 arm D indicate a immune response rate of 55% (12/22) with 95%CI(32, 76%) satisfy this definition. Accrual of a total of 24 eligible participants provides 80% power to test for a null immune response rate of 55% vs an alternative immune response rate of 80% was chosen to be above the upper limit of the CI to determine that the addition of ipilimumab improved immune response. At study conclusion the null hypothesis will be rejected and the treatment considered worthy of further study if at least 18/24 (75%) eligible participants experience an immune response.

Maximum target sample size is estimated to be 27 participants, which assumes a 10% dropout/ineligibility/lost to follow-up adjustment. Accrual to cohort 3 is expected to accumulate the most participants, at approximately 10 per year, followed by cohort 2 at 3-5 per year, and cohort 1 at 1-3 per year. Therefore, total accrual is estimated at approximately 16 participants per year, therefore, accrual to the study should be completed in less that two years.

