# Table 8: Stopping Guidelines for DLTs

#### 8.6 Analyses

Study populations and evaluation criteria are noted in Section 8.2. Adverse events will be summarized by frequency and magnitude of event. Incidence of DLTs will be monitored against the safety bounds above. The bounds are non-binding, and provide a guideline that may result in study modification or closure. Participants in cohorts 1 and 2 will be assessed for clinical response and will be classified by disease control by week 12 and at final assessement. DCR will be estimated along with a 95% confidence interval around the point estimate.

Immune response will be measured based upon the methods in Section 7.9. The criteria for defining immune responses have been reported for ELIspot assays (34). The circulating CD4+ T cell response rate to 6MHP peptides in participants treated with 6MHP vaccine plus ipilimumab will be assessed at each time noted in the study calendar. Maximum response over all time periods will be used to estimate the overall CD4+ T cell response. Other measures assessed over time in the blood include epitope-spreading for circulating CD8+ T cells reactive to a panel of defined melanoma antigens, and production of serum IgG reactive to 6MHP. Assessments in the tumor microenvironment include assessment for of CD8+ and/or CD4+FoxP3neg T cells into melanoma. Each participants experiencing an event (immune response, IgG antibody response to 6MHP, presence of CD8+ T cell infiltrates into the tumor (a subset), etc) will be estimated along with 95% confidence intervals. Repeated measure models will be explored to estimate changes over time in interval measurements in the blood and tissue.

Additionally, for cohort 3 only, estimates of immune response within the cohort will be estimated. We expect accrual of at least 15 eligible participants to cohort 3. At study conclusion, if 12/15 (80%) eligible participants satisfy the definition of immune response in cohort 3 then a 90%CI for immune response rate of 80% is (56%, 94%) which would support that immune response rate has improved in that cohort specifically.

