# 9.12 Monitoring Plan

9.12.1 The University of Virginia Cancer Center Data and Safety Monitoring Committee (CC DSMC) will provide oversight of the conduct of this study. The CC DSMC will report to the UVA Protocol Review Committee (PRC).

- 9.12.2 The UVA CC DSMC will review the following:
  - All adverse events
  - Audit results
  - Application of study designed stopping/decision rules
  - Whether the study accrual pattern warrants continuation/action
  - Protocol violations
- 9.12.3 The UVA CC DSMC will meet every month for aggregate review of data. Tracking reports of the meetings are available to the PI for review. Issues of immediate concern by the DSMC are brought to the attention of the sponsor (and if appropriate to the PRC and IRB) and a formal response from the

sponsor is requested. Per the UVA Cancer Center NIH approved institutional plan, this study will be audited approximately every 6 months.

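### Section 8.5: Table 8 departs from its own SPRT line at 16 participants, and the nominal 10%/10% errors are not what an upper-only bound capped at 27 attains (about 4.5% and 45%)

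*Combined protocol and SAP*

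**What the plan says.** Section 8.5 monitors DLTs with a sequential probability ratio test defined as "a SPRT contrasting a 15% versus 30% DLT rate, with nominal type I and II errors of 10% and 10%, respectively". It adds that "The slope of the parallel lines for monitoring is 0.219 and the intercept for the upper bound is 2.476" and that "Only the upper boundary will be used for monitoring to protect against excessive failure rates". Table 8 turns the line into integer bounds: at least 4 DLTs for 4-6 participants, 5 for 7-11, 6 for 12-15, 7 for 16-20, 8 for 21-25 and 9 for 26-27.

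Three other sections set how the bound is used:

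- Section 8.3: "Maximum target sample size is estimated to be 27 participants".
- Section 8.2.1: "The proposed safety bound will be applied overall and within cohort".
- Section 8.6: "The bounds are non-binding, and provide a guideline that may result in study modification or closure". For the largest cohort it says "We expect accrual of at least 15 eligible participants to cohort 3".

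The nominal pair of errors is the only performance information given for the bound. No probability of crossing is stated, either overall or by cohort.

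**The concern.** There are two separate points.

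The first is an internal contradiction. A team working from the formula and a team working from the table would act differently on 6 DLTs among 16 participants.

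The second matters more. Wald's error rates apply to a test that runs between an upper and a lower boundary until one is crossed, with no cap on sample size. Dropping the lower line and stopping at 27 changes both errors. The type I error falls, which is harmless. The type II error rises, and for a safety bound that is the error of concern.

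Safety is a primary objective. Section 8.2.1 says stopping rules were included because ipilimumab combined with each of two other vaccines had produced relatively high rates of hypophysitis. A DSMC member who sees only the 10% type II figure could take a bound that has not been crossed as stronger evidence against a 30% DLT rate than it is.

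**Working it through.** **Inputs.** From section 8.5: p0 = 0.15, p1 = 0.30, alpha = beta = 0.10, upper line only, and the Table 8 bounds. From section 8.3: a maximum of 27.

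**Step 1: reproduce the line.**

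- D = ln[p1(1-p0) / (p0(1-p1))] = ln[(0.30 x 0.85)/(0.15 x 0.70)] = 0.8873
- Slope = ln[(1-p0)/(1-p1)] / D = ln(0.85/0.70)/0.8873 = 0.2188, stated as 0.219
- Upper intercept = ln[(1-beta)/alpha] / D = ln(9)/0.8873 = 2.476, as stated

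**Step 2: compare the line with Table 8.** The bound at n is the smallest integer at or above 2.476 + 0.219n. Around the discrepancy:

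| n | Line | Bound from line | Table 8 |
|---|---|---|---|
| 15 | 5.761 | 6 | 6 |
| 16 | 5.980 | 6 | 7 |
| 17 | 6.199 | 7 | 7 |

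The unrounded line gives 5.977 at n=16, so rounding of the coefficients is not the cause. Nearest-integer rounding also gives 6 at n=16, and it breaks many other rows. The other 23 sample sizes from 4 to 27 agree.

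**Step 3: attained crossing probabilities.** Carry the binomial distribution of the DLT count forward one participant at a time, and remove as crossed any path at or above the bound. DLTs are taken as independent, with a check after every participant. To n=27:

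| True DLT rate | Table 8 as printed | n=16 set to the line |
|---|---|---|
| 15% | 4.5% | 4.8% |
| 20% | 15.3% | 15.9% |
| 30% | 55.4% | 56.0% |
| 35% | 74.6% | 75.0% |
| 40% | 87.9% | 88.2% |
| 50% | 98.5% | 98.5% |

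At a 30% rate the miss probability is 100 - 55.4 = 44.6% as printed, or 44.0% on the line. A simulation of 200,000 trials of the printed table gave 4.6% crossing at 15% and 55.3% at 30%.

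**Step 4: where the gap comes from.** The open two-boundary SPRT on these lines attains 7.7% and 9.3%, close to nominal. Its expected sample size is 31.6 at a 15% rate and 28.3 at 30%, both above 27. The upper line alone at a 30% rate crosses with probability 71.4% by n=40 and 85.4% by n=60, and first reaches 90% at n=74. The shortfall comes mainly from the cap at 27.

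**Step 5: effect of the n=16 cell.** At a 30% rate, setting it to the line raises cumulative crossing from 31.7% to 36.8% at n=16 (5.1 points). The difference is 1.2 points at n=20 and 0.6 at n=27.

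**Step 6: within cohort, 30% rate.** Cohort 3 at n=15: 31.7%. The plan fixes no size for cohorts 1 and 2. If cohort 3 takes 15 of 27, the other two share 12. For assumed sizes the crossing probability is 3.1% (n=5), 7.0% (n=7), 8.7% (n=8), 11.9% (n=9) and 16.5% (n=10).

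**The case against.** The arithmetic is not in dispute. The case for leaving the text alone rests on four points.

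- **The document calls the errors nominal and says openly that only the upper line is used.** It never claims 90% power to detect a 30% rate, and the sample size was set for immunogenicity. This stands: the slope and intercept are not wrong, and the second point is a missing statement of attained performance. But the nominal pair is the only figure given, and the word does not tell a reader that the type II error is more than four times larger.
- **The consequence is limited.** The bound is a guideline, a crossing suspends accrual for review, and the committee reviews all adverse events: "The UVA CC DSMC will meet every month for aggregate review of data". Rates of 40% and 50% are caught 88% and 98.5% of the time. This also stands and keeps the point moderate. A guideline that relies on judgement still needs its users to know what not crossing it means.
- **The attained figures depend on the look schedule and final sample size, which the plan leaves partly open.** DLTs are followed to 30 days after the last vaccination, nominally day 85 + 30 = 115, so some participants will be pending at any look. If accrual ends at 24, detection at 30% is 50.6%. Looks only at the first sample size of each row plus n=27 give 45.2%. Looks only at row ends give the same 55.4%, because the bound is constant within a row. Table 8 covers every n from 4 to 27 and section 9.10 describes continuous monitoring, so a check after each participant is the natural reading. The alternatives mostly lower detection.
- **The n=16 cell is trivial, and nothing says whether the table or the line governs.** It is small. The plan should still say which applies, and both sets of figures are given above.

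**Conclusion.** Both points hold. Table 8 contradicts the stated line at n=16 (7 against 6) and agrees everywhere else. The effect on the overall crossing probability is 0.2 points at a 15% rate and 0.6 points at 30%.

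Separately, the rule as written attains a type I error of about 4.5% and a type II error of about 45%, against a nominal 10% each. The type I departure is conservative. The type II departure is material and unreported. Depending on the final sample size and look schedule, detection of a 30% DLT rate lies between about 45% and 56%. Within cohorts the bound is at best a coarse signal.

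These figures assume independent DLTs, complete DLT status at each look, and a crossing counted once and treated as final. The sizes used for cohorts 1 and 2 are assumptions. This should be fixed; it does not undermine the design.

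**What to change.** 1. Reconcile Table 8 with the line and say which governs. Following the line, the two affected rows become 12-16: at least 6, and 17-20: at least 7. If the printed table is kept instead, say that it departs from the line at n=16.
2. Beside the nominal errors, state the attained crossing probabilities for a maximum of 27. On the line these are about 4.8% at a 15% rate, 56.0% at 30% and 88.2% at 40%. For the printed table they are 4.5%, 55.4% and 87.9%. State the look schedule they assume.
3. Add one sentence that within-cohort detection at a 30% rate is below 10% for cohorts of 8 or fewer and about 32% for cohort 3 at 15 participants.

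The slope and intercept need no change. The cost is one table row and two or three sentences, with no extra participants. Moving n=16 to the line raises the chance of a false suspension at a 15% rate from 4.5% to 4.8%. The bound will also look weaker on paper than 10%/10% suggests, which is the accurate picture.
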